7.3.2.2.2 Demographic and Clinical Characteristics

In support of the secondary objectives, we will report the following patient demographic, and clinical characteristics in the study population. Pending data availability, related variables may be adjusted and will be finalized in the case report form.

Demographics at Baseline

- Year and month of birth
- Age
- Gender

- Height and weight
- Smoking
- Alcohol use
- Geographic region (e.g., rural/urban, eastern/middle/western)
- Type of medical insurance
- Insurance coverage for posaconazole (injection and/or tablet formulations)

Clinical Characteristics

- Baseline disease(s)
- Infection history
- Treatment history
- Risk factor(s) related to treatment outcome, e.g. Allogeneic hematopoietic stem cell transplant (HSCT); Relapsed leukemia, undergoing salvage chemotherapy; Liver transplant recipients; all forms of immunocompromise (HIV infection; any solid organ transplantation; high dose corticosteroid therapy such as for chronic pulmonary or autoimmune diseases), etc

Examination

• Relevant examinations information for the diagnosis of proven, probable, possible IA and the treatment outcome assessment (e.g. galactomannan [GM] test, histopathology, cytopathological examination, needle biopsy record, imaging examination, bronchoscopy examination, antigen detection, etc.)

Diagnosis History

- IA diagnosis type (proven, probable, possible)
- IA infection site(s)
- Date of diagnosis
- Death date

PRODUCT: MK5592	PROTOCOL/AMENDMENT VERSION NO.: 2
REVOPS ID NO: NIS102646	CORE DRC APPROVAL DATE: 18-SEP-2024
EPIDEMIOLOGY NO.(PE STUDIES ONLY): EP08047.004	

7.3.2.2.3 Treatment Patterns

In support of the secondary objectives, we will report the following treatment patterns in the study population. Pending data availability, related variables may be adjusted and will be finalized in the case report form.

- First line/Salvage treatment
- Posaconazole regimen (dosage, duration)
- Combination therapy situation (list what agent(s) used, AmphoB, echinocandins, etc)
- Treatment related outcome (survival, death, complete response, partial response, stable response, progression of fungal disease)

Discontinuation of posaconazole Treatment (if applicable)

- Posaconazole discontinuation (yes/no)
- Stop date of posaconazole (date when previously dispensed medications were expected to be finished or documented by the clinician in medical records)

When a patient was considered to have discontinued posaconazole treatment, the below categories will be classified as the reason for discontinuation, if applicable, and the classification will be based on the descrition of the treating physician:

- Resistance (lack of response/persistent IA or progression of IA)
- Intolerance (patients discontinued because of toxicity related to Posaconazole; record clinical description/diagnosis once happens)
- Drug-drug interactions (e.g., potential interations, describe the product(s) and rationale to discontinue POSA therapy; actual interactions, describe products impacted and any associated AE)
- Financial (e.g., insurance coverage)
- Others (cannot be free text)
- Not documented

7.3.3 Covariates

Demographic and clinical characteristics will be collected at baseline in the study population if data is available (see 7.3.2.2.2).

PRODUCT: MK5592	PROTOCOL/AMENDMENT VERSION NO.: 2
REVOPS ID NO: NIS102646	CORE DRC APPROVAL DATE: 18-SEP-2024
EPIDEMIOLOGY NO.(PE STUDIES ONLY): EP08047.004	

7.4 Data Sources

Relevant patient-level information will be collected from multiple information systems, including EMR,paper medical records, Hospital Information System (HIS), Laboratory Information System (LIS), and routine patient management material from clinicians in selected hospitals. Medical records from other hospitals can be collected as needed The databases contain both inpatient and outpatient data.

For patient with retrospective data collection missing with dead or alive status in medical record, a follow up to confirm the dead or alive status through day 42 is required. Death certificate information or the follow-up contact/report/record by investigator would be the data sources.

All data will be collected with the use of a standardized case report form.

	36
PRODUCT: MK5592	PROTOCOL/AMENDMENT VERSION NO.: 2
REVOPS ID NO: NIS102646	CORE DRC APPROVAL DATE: 18-SEP-2024
EPIDEMIOLOGY NO.(PE STUDIES ONLY): EP08047.004	

7.4.1 Study Procedures

This study administered in a non-interventional setting. The study protocol will be submitted for approval by the institutional review board (IRB)/ethics review committee (ERC). Figure 2 shows the procedures of eligible patients enrollment.

	37
PRODUCT: MK5592	PROTOCOL/AMENDMENT VERSION NO.: 2
REVOPS ID NO: NIS102646	CORE DRC APPROVAL DATE: 18-SEP-2024
EPIDEMIOLOGY NO.(PE STUDIES ONLY): EP08047.004	

Given that the study design involves prospective and retrospective data collection, the participating practitioner will obtain informed consent from patients included in prosepective data collection and submit the study to the IRB/ERC to let IRB/ERC determine whether the patients including in retrospective data collection qualifies to waive for informed consent. While doing retrospective data collection, if a follow up is need for patients to collect dead or alive status through Day 42, the informed consent should be obtained.

7.5 Study Size

All eligible IA patients will be identified and recruited from the March 2022 to Dec 2024.

55-70 cases with posaconazole treatment are expecting to be enrolled during the recruitment period for primary and secondary objectives (30-40 cases for primary objective). The estimation of sample size is based on market supply estimation and the RCT enrollment experience. The final sample size will depend on the number of patients eligible for the study in the study period. No hypothesis test and power calculation in this study. The total sample size in the final study report may be less. See Table 2, assuming 15%-50% of all-cause mortality observed through Day 42 for primary objective, the half-width of 95% confidence interval (CI) will range from 12.1%-18.7%.

Estimated number for primary objective participants	Number of Death (%)	Two-Sided 95% Confidence Interval	Half-width of 95% Confidence Interval
N=30	4.5 (15.0)	(4.7, 32.7)	14
	6 (20.0)	(7.7, 38.6)	15.4
	9(30.0)	(14.7, 49.4)	17.3
	12 (40.0)	(22.7, 59.4)	18.4
	15 (50.0)	(31.3,68.7)	18.7
N=40	6 (15.0)	(5.7, 29.8)	12.1
	8(20.0)	(9.1, 35.6)	13.3
	12(30.0)	(16.6, 46.5)	15
	16 (40.0)	(24.9, 56.7)	15.9
	20 (50.0)	(33.8, 66.2)	16.2

 Table 2
 Two-Sided 95% Confidence Intervals for All-cause Mortality

^a Based on the two-sided exact confidence interval of a binomial proportion (Clopper and Pearson, 1934).

7.6 Data Management

All data collected for the study should be recorded accurately, promptly, and legibly. For primary data collection, the investigator or qualified designee is responsible for recording and verifying the accuracy of subject data. For data not obtained from a primary source (i.e., secondary data, such as claims and electronic health records), the investigator is responsible

	38
PRODUCT: MK5592	PROTOCOL/AMENDMENT VERSION NO.: 2
REVOPS ID NO: NIS102646	CORE DRC APPROVAL DATE: 18-SEP-2024
EPIDEMIOLOGY NO.(PE STUDIES ONLY): EP08047.004	

for reviewing data quality and relevance to the best of the investigator's knowledge. By signing this protocol either electronically or written, the investigator confirms that the quality and relevance of data has been assessed to meet the minimum requirements for all study objectives.

If this study has been outsourced, the institutional policies of the supplier should be followed for development of data management plans. However, the supplier should ensure compliance with Good Pharmacoepidemiology Practice, and all applicable federal, state, and local laws, rules and regulations relating to the conduct of the study.

Data Management Software and Hardware:

Electronic Data Capture (EDC) System will be used in this study to collect and clean clinical data.

Туре	Software System & Version
Clinical Database	Oracle® Clinical RDC Onsite 4.6.2
Data Entry	Oracle® Clinical RDC Onsite 4.6.2
Data Validation	Oracle® Clinical RDC Onsite 4.6.2
Medical Coding	Coding out of system: Programming

Statistical analysis is performed using SAS (version 9.4 or above) software.

Description of Data Preparation and Methods for Data Retrieval and Collection:

A case report form will be used for data collection. All data management activities including data capture, data storage, data cleaning, data security, and system backup processes will be undertaken by qualified personnel and will follow all procedures detailed in a separate "Data Management Plan".

7.7 **Programming Quality**

Not applicable.

7.8 Data Analysis

A descriptive analysis of the distribution of values abstracted for each variable will be provided. For the continuous variables we are interested, the values of mean/median, standard deviation (SD), min/max, interquartile range (IQR, including the first quartile [Q1] and third quartile [Q3]) will be calculated; the frequency and percentages will be calculated for these categorical variables. All analyses will be carried out using all available data. A participant with missing data on one variable will be used only in calculations that do not involve that variable.

	39
PRODUCT: MK5592	PROTOCOL/AMENDMENT VERSION NO.: 2
REVOPS ID NO: NIS102646	CORE DRC APPROVAL DATE: 18-SEP-2024
EPIDEMIOLOGY NO.(PE STUDIES ONLY): EP08047.004	

All analyses will use SAS (SAS Institute Inc., Cary, North Carolina). Detailed statistical analysis plan (SAP) and corresponding mock-up tables/figures/listings will be described separately prior to the commencement of any analyses.

All analysis detailed will be described in a separate "Statistical Analysis Plan". Key points are listed below.

7.8.1 **Primary Objective**

The primary objective is to assess the all-cause mortality of using posaconazole for proven, probable, possible IA patients. The all-cause mortality will be calculated with 95% CI.

Total all-cause mortality=number of total IA patients who die through Day 42/number of all IA patients (proven, probable, possible) included in the study with dead or alive status reported x 100%.

All-cause mortality by treatment line=number of IA patients by treatment line who die through Day 42/number of IA patients by treatment line (proven, probable, possible) included in the study with dead or alive status reported x 100%.

The analysis will be stratified by method of data collection: prospective vs. retrospective.

The following subgroupanalysis may be conducted depending on data availability:

- 1. Treatment duration (e.g. group by median treatment duration, etc);
- 2. Patients who only receive Posaconazole injection vs patients who receive Posaconazole injection then Posaconazole tablet;
- 3. Risk factors for mortality and poor outcome (Allogeneic hematopoietic stem cell transplant (HSCT); Relapsed leukemia, undergoing salvage chemotherapy; Liver transplant recipients)
- 4. IA at sites: Pulmonary IA vs others (sinus/upper respiratory involvement or disseminated disease to other organs).

The following sensitivity analysis may be conducted depending on data availability:

Merge analysis of data from both prospective and retrospective collection.

08R 565

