7.2.5.5 Patient Index Date and Specific Treatment Assessment Durations

Patient index date is defined as the date of the first treatment of posaconazole injection and/or tablet formulations.

	30
PRODUCT: MK5592	PROTOCOL/AMENDMENT VERSION NO.: 2
REVOPS ID NO: NIS102646	CORE DRC APPROVAL DATE: 18-SEP-2024
EPIDEMIOLOGY NO.(PE STUDIES ONLY): EP08047.004	

Specific treatment assessment duration for different outcomes are summarized as follows:

- Assessment for all-cause mortality for IA will occur at Day 42. Treatment may continue beyond Day 42.
- Assessment for overall response will occur at the end of treatment (for both first line and salvage treatment). Patients may continue treatment beyond 12 weeks (84 days) however assessment for response to therapy will occur at 84 days for such patients. For patients who receive less than 12 weeks of treatment, assessment will occur at the end of posaconazole treatment.

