7.8.2 Secondary Objectives

7.8.2.1 Overall response rates of posaconazole injection and/or tablet by treatment line at the end of posaconazole treatment

The secondary objective is to assess the overall response rates of using posaconazole for proven or probable or possible IA patients by treatment line. The Numerator is the success response of posaconazole which include survival followed by either complete response (CR) or partial response (PR) definition by treatment line (first line or salvage). The overall response rates at the end of posaconazole treatment will be described by percent with 95% CI in the patients with proven or probable or possible IA patients by treatment line.

Overall response rates (ORRs)=(number of patients with CR or PR) by treatment line (first line or salvage treatment)/ number of IA patients included in the study with available evidence on treatment response at the end of treatment by treatment line (first line or salvage treatment) x 100%.

The analysis will be stratified by method of data collection: prospective vs. retrospective.

The following subgroup analysis may be conducted depending on data availability:

- 1. Treatment duration;
- 2. Patients who only receive posaconazole injection vs patients who receive posaconazole injection then posaconazole tablet;
- 3. Risk factors for mortality and poor outcome (Allogeneic hematopoietic stem cell transplant (HSCT); Relapsed leukemia, undergoing salvage chemotherapy; Liver transplant recipients; HSCT+Hematologic Malignancy vs. all other immunocompromised vs. No recorded risk factor (if any));
- 4. IA at sites: Pulmonary IA vs others (sinus/upper respiratory involvement or disseminated disease to other organs);
- 5. Methods of clinical response definition: guideline vs. investigator judgment.

The following sensitivity analysis may be conducted depending on data availability:

Merge analysis of data from both prospective and retrospective collection.

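### Optional mortality subgroups by observed treatment duration and by later switch to tablet are truncated or blocked by death, so they favour longer treatment and switching even with no effect

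*Protocol*

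**What the plan says.** Protocol section 7.2.5.5 sets time zero: "Patient index date is defined as the date of the first treatment of posaconazole injection and/or tablet formulations". Sections 7.3.2.1 and 7.8.1 count all deaths through Day 42.

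Section 7.8.1 then lists subgroup analyses of mortality that may be done if the data allow. Item 1 is "Treatment duration (e.g. group by median treatment duration, etc"). Item 2 is "Patients who only receive Posaconazole injection vs patients who receive Posaconazole injection then Posaconazole tablet".

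Section 7.8.2.1 reuses both for overall response: treatment duration is item 1, and item 2 is "Patients who only receive posaconazole injection vs patients who receive posaconazole injection then posaconazole tablet". Table 1 in section 7.3.2.2.1 classes death during the evaluation period as failure, and section 7.3.2.2.3 lists lack of response or progression as a reason for stopping.

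On size, section 7.5 expects "30-40 cases for primary objective", "assuming 15%-50% of all-cause mortality observed through Day 42 for primary objective", and states "No hypothesis test and power calculation in this study". Immortal time bias is named once, in section 7.10, for who can be reached for consent and for patients with unknown status. Neither that text nor section 7.8 gives a landmark, a planned-duration definition or a caution for these subgroups.

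**The concern.** Both groupings are settled after the index date, over the same days in which deaths are counted. A patient who dies on Day 15 has at most 15 days of treatment and tends to fall in the shorter group. A patient joins the injection-then-tablet group only by living long enough to be switched, and anyone on injection who dies before a switch is counted as injection only. The outcome therefore helps to decide the group.

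At stake is how the subgroup tables will be read. They would show lower mortality with longer treatment and with step-down to tablet whatever the drug does, and in a cohort of 30 to 40 the duration gap can be large enough to look convincing. Item 2 also has no place for tablet-only patients, although the study exposure includes them.

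**Working it through.** **1. The plan's own figures.** Table 2 is "Based on the two-sided exact confidence interval of a binomial proportion (Clopper and Pearson, 1934"). All ten rows reproduce to 0.1 point. For example, 12/40 gives 16.6%-46.5% and a half-width of 15.0. The protocol gives no figure for the subgroups.

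**2. Model with no effect.**
- From section 7.5: N = 40 and Day-42 mortality m of 15%, 30% or 50%. From the eligibility rule: every patient is alive and treated to Day 7.
- Assumed, because the protocol does not give it: a constant death hazard after Day 7, λ = −ln(1−m)/35, that is 0.00464, 0.01019 and 0.01980 per day. Planned course length and switch day are independent of death.
- Observed duration = min(planned duration, time to death), split at the median within each simulated study.

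**3. Duration subgroup, by hand.** Suppose all planned courses last at least 42 days. Every patient who dies before Day 42 then has a shorter duration than every patient who does not. If m is below 50%, all mN deaths fall in the shorter N/2, so mortality is 2m against 0. At m = 30% and N = 40 that is 12/20 = 60% against 0/20 = 0%. The exact intervals are 36.1%-80.9% and 0%-16.8%, which do not overlap.

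**4. Duration subgroup, simulated** (mortality, shorter vs longer half):

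| Planned course (days, uniform) | m = 15% | m = 30% | m = 50% |
|---|---|---|---|
| 42-84 | 29.9% vs 0% | 59.9% vs 0% | 93.6% vs 6.0% |
| 14-84 | 28.9% vs 1.0% | 54.2% vs 6.2% | 77.8% vs 22.3% |
| 7-84 | 28.1% vs 2.0% | 51.3% vs 8.9% | 73.8% vs 25.8% |
| 7-42 (range worded in 7.1 for the primary set) | 21.5% vs 8.6% | 41.3% vs 19.2% | 63.9% vs 36.1% |

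The gap runs from 21.5 − 8.6 = 12.9 points to 93.6 − 6.0 = 87.6 points.

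**5. Switch subgroup.** Assume half of patients intend to switch, on a day uniform from Day 7 to Day 7+L, and that treatment does not stop earlier for other reasons. The chance that an intending patient lives to switch is q = (1 − e^(−λL))/(λL). Mortality among switched patients is 1 − (1−m)/q. With p = q/2 switched, mortality in the rest is (m − p × switched mortality)/(1 − p).

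| Switch window | m | q | Injection only | Switched | Gap (points) |
|---|---|---|---|---|---|
| Days 7-21 | 15% | 0.968 | 17.6% | 12.2% | 5.4 |
| Days 7-28 | 15% | 0.953 | 18.8% | 10.8% | 8.0 |
| Days 7-28 | 30% | 0.900 | 36.4% | 22.2% | 14.1 |
| Days 7-28 | 50% | 0.818 | 57.7% | 38.9% | 18.8 |

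The window matters. With L = 35 (Days 7-42) the same formulas give gaps of 13, 23 and 30 points at the three mortality levels; a window closing before Day 21 would give less than the first row. If every patient intends to switch, the gap at m = 30% (Days 7-28) is 56% vs 23% for planned courses of 7-84 days and 100% vs 22% for courses of at least 42 days.

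**6. Response (7.8.2.1).** Assume 60% of patients alive at assessment respond. Shorter vs longer duration, from death alone, at m = 15%, 30% and 50%:
- Salvage (planned 7-84 days): 46.6% vs 54.2%, 36.2% vs 47.0%, 25.6% vs 35.6%.
- First-line (42-84 days, so no deaths before Day 42 in the set): 52.2% vs 57.0%, 44.7% vs 52.8%, 35.3% vs 46.3%.

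These are gaps of about 5 to 11 points. If half of the salvage non-responders also stop between Day 7 and Day 28, the salvage figures become 34.6% vs 66.3%, 27.4% vs 55.5% and 20.8% vs 40.8%, gaps of 20 to 32 points.

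**7. Does the remedy work?** Under the same model, splitting by planned duration gives equal mortality in both halves (about 30% each at m = 30%). A Day-14 landmark by switch status at that day gives 12.2% vs 12.2%, 24.9% vs 24.8% and 42.7% vs 42.7%. The expected value is 1 − (1−m)e^(7λ) = 12.2%, 24.8% and 42.6%.

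**The case against.** The strongest case on the other side concerns weight and size.

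- The subgroups may never be done. They are descriptive, with no test planned, and detail is left to a separate SAP. The median split is only an example, so a landmark could still be set there. All this lowers the priority. It does not make the listed groupings sound: they are written into the protocol without a caution, and section 10 ties publications to its pre-specified analyses.
- A reader might infer that death alone decides group membership, or take one simulated gap as the bias to expect. The documents support neither. Planned course length also shapes duration, and the protocol gives no distribution for it; that is why the gap spans 13 to 88 points.
- The switch artefact is moderate when only half of patients intend to switch, and small beside the imprecision of a 40-patient cohort. That stands. The most extreme contrasts need every patient to intend to switch.
- A reader might infer equally large distortions in response. First-line response requires 42 to 84 days of treatment, so earlier deaths are outside that set, and death alone moves response by only about 5 to 11 points. Larger gaps need early stopping for non-response at an assumed rate.
- Item 2 can be read as a narrow step-down contrast. Tablet-only patients remain in the total, by-line and treatment-pattern results, so their absence from this one table is a lesser point.

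**Conclusion.** The point holds for the mortality subgroups in section 7.8.1. Observed duration and later switch are defined after the index date and are truncated or blocked by death, so they show lower mortality with longer treatment or a switch when there is no effect. The direction does not depend on the details of the model; the size does. It is about 13 to 88 points for duration over 15%-50% mortality and planned courses between 7 and 84 days. For the switch it is about 5 to 19 points if half intend to switch between Day 7 and Day 21 or 28. Constant hazard, planned durations, switch windows and the 60% response rate are assumptions, not protocol figures.

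The groupings in 7.8.2.1 are affected to a smaller degree, mainly for salvage. Nothing here supports reading the total or by-line mortality estimates as biased by these subgroups; neither uses the groupings. This is a change that should be made before the subgroups are analysed, not a fault in the primary analysis.

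**What to change.** In 7.8.1, delete the median split of observed duration, or replace it with a landmark analysis: take patients alive and followed at a fixed day, group them by exposure up to that day, and count only later deaths. Handle the injection-to-tablet switch by the same landmark, or group by formulation at the index date. The second option answers a different question from step-down, but it uses baseline information and places tablet-only patients.

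In 7.8.2.1, make the same change to the switch item. Drop the duration item, landmark it, or report it descriptively without comparing the groups.

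The cost is protocol and SAP wording and some loss of numbers. With N = 40, 30% mortality and a Day-14 landmark under the model above, 40 × e^(−7 × 0.01019) ≈ 37 patients remain, with about 12 − 3 = 9 later deaths. With N = 30 and 15% mortality, about 29 remain with 3 to 4 later deaths. Section 7.3.2.2.3 lists regimen, duration and stop date but not the date of a formulation change, so the case report form must capture that date if the landmark by switch is used.

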7.1 Study Design

The study does not involve any interventional measurements, e.g., receiving posaconazole injection and/or tablet, laboratory test for IA diagnosis. Under this protocol, all patients accepted posaconazole injection and/or tablet previously in the course of routine clinical practice.

This is a multicenter observational study involving prospective (Planned: Oct 2023-Dec 2024) and retrospective (Planned: Mar 2022- Oct 2023) data collection from target hospitals using a case report form during the planned recruitment period (Oct 2023-Dec 2024).

Chinese adult IA patients (\geq 18 years old) who have been treated with posaconazole for at least 7 days in accordance with NMPA's approved product information are potential subjects for the study.

After inclusion/exclusion criteria check: (1) The patients who have continued posaconazole treatment for 7 to 42 days and have dead or alive status available through day 42 will be evaluated for primary objective. (2) The patients who have continued posaconazole as first line treatment for 42 to 84 days and have treatment response data available (success or failure at the end of treatment or at a maximum duration of 84 days) will be evaluated for secondary objectives. (3) The patients who have continued posaconazole as salvage treatment for 7 to 84 days and have treatment response data available (success or failure at the end of treatment response data available (success or failure at the end of treatment for 7 to 84 days) will be evaluated for secondary objectives. The demographic, clinical characteristics and treatment patterns will be described in this study.

Information will be collected by using a case report form during the planned recruitment period (Oct 2023-Dec 2024) including but not limited to outpatient or inpatient medical records, lab reports, prescription records, etc., by qualified investigators.

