7.3.2.1 Primary Outcomes

The primary outcome is all-cause death among proven, probable, possible IA patients who received at least 7 days of posaconazole injection and/or tablet formulations treatment through Day 42.

Death is defined as a patient with death is recorded in the medical history or death certificate can be provided through Day 42 or within Day 42. (Data cources see 7.4)

Patients with missing or 'unable to determine' dead or alive status through Day 42 will be excluded.

PRODUCT: MK5592	PROTOCOL/AMENDMENT VERSION NO.: 2
REVOPS ID NO: NIS102646	CORE DRC APPROVAL DATE: 18-SEP-2024
EPIDEMIOLOGY NO.(PE STUDIES ONLY): EP08047.004	

Secondary Outcomes 7.3.2.2

7.3.2.2.1 **Clinical response**

The clinical response of proven, probable, possible IA patients who received posaconazole injection and/or tablet formulations treatment as the first line or salvage treatment at the end of posaconazole treatment.

Clinical responses will be defined by using the 2017 Chinese guidelines for the diagnosis and treatment of invasive fungal disease in patients with hematological disorders and cancers (the fifth version) (Table 1) or by the investigator⁷(s).

⁷Considering the low compliance with guidelines in real-world clinical practice, it is possible that there may be insufficient information from medical record to support the definition of clinical response according to the guideline (Table 1). Therefore, investigator's professional judgment could be used to define the clinical response. The subgroup analysis by the methods of clinical response definition (guideline vs. investigator's professional judgment) will be conducted depending on data availability. (see 7.7.2.1)

See Table 1 for the definitions for clinical response from the 2017 Chinese guidelines for the diagnosis and treatment of invasive fungal disease in patients with hematological disorders and cancers (the fifth version). The Chinese guidelines are consistent with the 2008 EORTC/MSG guidelines.

Table 1 Clinical Response Definitions from the 2017 Chinese guidelines for the diagisnos and treatment of invasive fungal disease in patients with hematological disorders and cancers (the fifth version).

Outcome, Response	Criteria
Success	

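### The treatment-duration subgroup of Day-42 mortality groups patients by a quantity that death cuts short, so the longer-treated group is biased towards lower mortality even if duration has no effect

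*Protocol*

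**What the plan says.** Section 7.8.1 names subgroup 1 of the primary outcome as "Treatment duration (e.g. group by median treatment duration, etc". The subgroup analyses "may be conducted depending on data availability".

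Three other statements fix how duration relates to the outcome:

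- Time zero (Section 7.2.5.5): "Patient index date is defined as the date of the first treatment of posaconazole injection and/or tablet formulations".
- Outcome (Section 7.3.2.1): all-cause death in patients "who received at least 7 days of posaconazole injection and/or tablet formulations treatment through Day 42".
- Overlap (Section 7.2.5.5): "Treatment may continue beyond Day 42". Section 7.1, however, describes the primary evaluation set as "The patients who have continued posaconazole treatment for 7 to 42 days and have dead or alive status available through day 42".

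Section 7.8.2.1 repeats "Treatment duration" as a subgroup of the overall response rate, without mentioning a median split. For that outcome, Section 7.2.5.5 states: "Assessment for overall response will occur at the end of treatment (for both first line and salvage treatment".

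Neither section sets a landmark, a time-varying exposure, a rule based on intended duration, or a caveat. Section 7.10 mentions immortal time bias only for the easier consent of survivors and for loss to follow-up. Its remedies, contacting relatives and close monitoring, do not bear on this subgroup.

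**The concern.** Observed duration is not a baseline characteristic. It builds up over the same days in which deaths are counted, and a patient who dies early will usually have a short duration because of the death. Early deaths therefore collect in the shorter group, while patients must survive long enough to enter the longer one.

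A two-row table of Day-42 mortality by duration would tend to show lower mortality with longer treatment whatever the drug does. In a report on effectiveness, that contrast invites a conclusion about length of treatment that the data cannot support. With no comparator and no adjustment planned, nothing else in the analysis would correct the table.

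**Working it through.** The plan gives no figure for this subgroup. Its nearest figure is Table 2 (Section 7.5), which supplies the mortality range. The exact binomial limits reproduce: half-width 12.06 points for 6/40 and 18.70 for 15/30, against the stated 12.1 to 18.7.

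**Inputs from the protocol.** Time zero at first dose (7.2.5.5); death through Day 42 with at least 7 days on drug (7.3.2.1); Day-42 mortality p of 15% to 50% and N of 30-40 (7.5); 7 to 42 days of treatment in the primary set (7.1).

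**Assumptions.** Constant hazard from the index date. Intended duration is uniform on a to b days and independent of the time of death, so duration has no effect. Observed duration is the smaller of intended duration and time to death.

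**Step 1: true mortality in the analysed set.** h = -ln(1 - p)/42. For p = 0.30, h = 0.3567/42 = 0.008492 per day. Given survival to Day 7, mortality by Day 42 is 1 - 0.70^(35/42) = 25.7%, whatever the intended duration.

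**Step 2: the median split.** The median observed duration m solves exp(-h(m - 7)) × (b - m)/(b - a) = 0.5. Patients with at least m days were alive at m, so their Day-42 mortality is 1 - exp(-h(42 - m)), or 0 if m is 42 or more. The halves are equal in size, so the shorter half has 2 × 25.7% minus the longer half's value.

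For 7-42 days, m = 22.1: exp(-0.008492 × 15.1) × 19.9/35 = 0.880 × 0.569 = 0.50. Longer half: 1 - exp(-0.008492 × 19.9) = 15.5%. Shorter half: 51.4 - 15.5 = 35.9%, against 35.7% by simulation.

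| Intended duration (assumed), p = 30% | m (days) | Longer half, formula | Simulated shorter vs longer |
|---|---|---|---|
| 7-21 days | 13.6 | 21.4% | 30.0% vs 21.5% |
| 7-42 days | 22.1 | 15.5% | 35.7% vs 15.5% |
| 7-84 days | 35.1 | 5.7% | 45.8% vs 5.7% |
| 14-84 days | 38.3 | 3.1% | 48.5% vs 3.0% |
| 7-84 days, only observed durations up to 42 days kept | not by formula | not by formula | 50.2% vs 36.3% |

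In the last row both halves exceed 25.7% because the restriction removes patients treated beyond Day 42, who are survivors. That lift comes from the set definition; the gap between the halves comes from the split.

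**Step 3: across the protocol's mortality range.**

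- Intended 7-42 days, p = 15%: h = 0.003869, m = 23.4; longer 1 - exp(-0.003869 × 18.6) = 6.9%, shorter 2 × 12.67 - 6.94 = 18.4%.
- Intended 7-42 days, p = 50%: h = 0.016504, m = 20.2; longer 1 - exp(-0.016504 × 21.8) = 30.2%, shorter 2 × 43.88 - 30.22 = 57.5%.
- Intended 14-84 days, simulated: 25.3% vs 0.0% at 15%, and 71.9% vs 15.8% at 50%.

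The direction is the same throughout.

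**Step 4: control.** Splitting the same simulated patients (14-84 days, p = 30%) at the median intended duration gives 25.7% vs 25.9%. The gap arises only from using observed duration.

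**Step 5: would a landmark rescue it?** A Day-14 landmark removes the bias: 21.1% vs 21.2% at p = 30% with intended 7-84 days. But only (14 - 7)/(84 - 7) = 9% of survivors have stopped by then, about 3 of 30-40 patients. With intended 14-84 days, essentially none have. It also drops (1 - 0.70^(7/42))/(1 - 0.70^(35/42)) = 0.0577/0.2571 = 22% of the analysed deaths.

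**Step 6: response rate.** Response is assessed when treatment ends, and death counts as failure (Table 1), so the outcome can help determine duration. This is clearest in salvage patients (7-84 days). First-line patients need 42-84 days, which narrows the range. Recovery may end treatment early, while a stable response, which counts as failure, may prolong it. These forces oppose each other, so no direction follows.

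**The case against.** The strongest reply is that little hangs on this table. It is optional, the median split is offered only as an example, no hypothesis is tested, and details are left to a separate statistical analysis plan. All of that is true and limits the weight of the point. But duration is a collected variable, so data availability is unlikely to block the analysis, and the protocol itself names the unsound split.

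Second, the size depends on assumed durations, and the widest gaps come from ranges that extend beyond the 7 to 42 days in Section 7.1. This stands, and is why a range is shown.

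Third, Section 7.3.2.2.3 lets the stop date be the expected end of dispensed supply, which can fall after death. A reader might infer that nobody who dies on Day 20 can have more than 20 days recorded. The documents do not support that as an absolute statement: the rule weakens the truncation without removing it.

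Fourth, real data may offset part of the bias, for instance if recovered patients stop early or sicker patients are treated longer. That makes the observed contrast less predictable, not valid.

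Finally, death dates, stop dates and reasons for discontinuation are collected, so an alert reader could suspect the artefact. It would be too strong to say that nothing in the study could reveal it, but those listings do not correct the table.

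**Conclusion.** The point holds for the primary-outcome subgroup. Grouping Day-42 mortality by observed duration biases the longer group towards lower mortality when duration has no effect. At 30% mortality from the index date, the spurious gap ranges from 8.5 points (30.0 - 21.5) to 45.5 points (48.5 - 3.0) over the scenarios shown, and is about 20 points (35.7 - 15.5) for intended durations of 7-42 days. These sizes rest on a constant hazard and assumed uniform durations; the direction was the same at 15% to 50% mortality.

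Two stronger readings are tempting and not supported. One is that mortality in the longer group must be exactly zero. It is essentially 0% only if patients treated beyond Day 42 are included and the median reaches 42 days; Section 7.1 points to a set that excludes them, and the stop-date rule allows exceptions. The other is that longer treatment will also look better for response. That subgroup is unsound as well, but the direction of its bias is not established.

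Total and by-line mortality estimates are not affected by this subgroup.

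**What to change.** Delete the treatment-duration subgroup from Sections 7.8.1 and 7.8.2.1. In the treatment-pattern tables, report duration descriptively by outcome (Day-42 deaths versus survivors; responders versus non-responders), with a note that death truncates duration.

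A landmark version should be added only if enough patients have stopped treatment by the landmark day, which is unlikely at N = 30-40.

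The cost is a wording change in the protocol, carried into the statistical analysis plan, and the loss of one optional table for each outcome.
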